**Version Number: v. 5.0**

**23 March 2021**

## Protocol Amendment History:

Version	Date	Description of Change	Brief Rationale
2.0	12/3/2020	Updated version date and number and table of content page numbers	Administrative update
2.0	12/3/2020	Added clinicaltrials.gov number to cover page (NCT04556591)	Added CT.gov posting number since it has been assigned
2.0	12/3/2020	In section 8.1.5.3, noted that the monthly surveys could also be given via interview format (in addition to the CareQOL app)	Provides flexibility with administration, especially with feasibility questionnaire which is the primary outcome measure
3.0	1/21/2021	Updated version date and number and table of content page numbers	Administrative update
3.0	1/21/2021	Updated sample size from "60" to "60 – 90" for the overall study sample, from "20" to "20-30" for each participant population, and from "10" to "10-15" for each arm within each participant population. Changes were made in sections 1.1 and 4.1.	We are over-recruiting to account for missing data
3.0	1/21/2021	Removed the criteria that the spinal cord injury needed occur when the person with SCI was at least 16 years old. Change was made in section 5.1.	The age at which the spinal cord injury was obtained is not important scientifically as long as the person with the SCI is currently an adult (at least 18).
4.0	2/3/2021	Updated version date and number and table of content pages numbers.	Administrative update.
4.0	2/3/2021	In section 5.1, the inclusion criteria were clarified to indicate that medical documentation was required for each condition.	Clarified that medical documentation is needed as an inclusion criteria.
5.0	3/23/2021	Updated version date and number and table of content page numbers	Administrative update
5.0	3/23/2021	Updated SOA (section 1.3) to include optional semi-structured interview for active group only	Added an optional semi-structured interview for intervention group to learn more about participant experiences and perceptions of the intervention messages
5.0	3/23/2021	Updated section 8.1.6 to include a description of the optional semi-structured interview	Added optional semi-structured interview (see above)
5.0	3/23/2021	Updated section 10.1.1.2 to describe consent procedure for optional semi-structured interview	Added optional semi-structured interview (see above)

5.0	3/23/2021	Updated section 10.1.2 to provide information on confidentiality and privacy related to optional semi-structured interview	Added optional semi-structured interview (see above)

## STATEMENT OF COMPLIANCE

This trial will be carried out in accordance with the United States (US) Code of Federal Regulations (CFR) applicable to clinical studies (45 CFR Part 46, 21 CFR Part 50, 21 CFR Part 56, 21 CFR Part 312, and/or 21 CFR Part 812) and research best practices. The PIs and all study team members who are responsible for the conduct, management, or oversight of NIH-funded clinical trials will complete Human Subjects Protection and best practices training.

The protocol, informed consent document, and all participant materials will be submitted to IRBMED, for review and approval. Approval of both the protocol and the consent documents will be obtained before any participant is consented. Any amendment to the protocol will be submitted for review and approval by IRBMED before the changes are implemented to the study. All changes to the consent form(s) will be IRB approved; a determination will be made regarding whether a new consent needs to be obtained from participants who provided consent, using a previously approved consent form.

## 1 PROTOCOL SUMMARY

### 1.1 SYNOPSIS

**Title:** Mobile Technology and Data Analytics to Identify Real-Time Predictors of Caregiver Well-Being

**Study Description:** Care partners (i.e., informal family caregivers) of individuals with health problems are faced with considerable physical and emotional stress, often with substantial negative impact on the health related quality of life (HRQOL) of both the care partner and care-recipient. Care partners may be suddenly thrust into this full-time role and are often unprepared. As responsibilities accumulate, they face emergent health risks, including anxiety, fatigue, isolation, sleep problems, and decreased physical activity. Indeed, there is growing recognition that these psychological, social, and physical risks inadvertently affect patient health and well-being (i.e., outcomes). Thus, it is imperative to develop novel interventions to support caregivers to ensure better patient outcomes.

Despite the growing awareness about the importance of caregiving with the aging U.S. population and evolving health-care system, very little action has been taken to understand and improve conditions for caregivers. Thus, family caregiving (i.e., care partners) is an urgent public health issue. With high risk for developing depression, insomnia, and stress-related disorders, care partners are an ideal population to target for early detection and intervention strategies to treat compromised well-being. While psychoeducation, skills training, or therapeutic counseling interventions can be effective for care partners, these interventions require intensive time and face-to-face commitment (with trained personnel), which can be prohibitive for an individual that is already overwhelmed by existing caregiving responsibilities and unable to make time for self-care.

In this study, we will examine the acceptability and feasibility of a data collection protocol that involves the delivery of a personalized self-management intervention to promote care partner self-care. This just-in-time adaptive intervention (JITAI) is an emerging intervention that incorporates passive mobile sensor data feedback (sleep and activity [step] data from a Fitbit®), and real-time self-reporting of HRQOL via study specific app called CareQOL to provide personalized feedback via app alert. The proposed trial will examine the acceptability and feasibility of the JITAI in three distinct groups of care partners: 1) care partners for persons with a chronic condition that was caused by a traumatic event (i.e., spinal cord injury [SCI]); 2) care partners for persons with a progressive, fatal neurodegenerative disease (i.e., Huntington disease [HD]); and 3) care partners for persons with an episodic cancer condition that requires intense, prolonged inpatient and outpatient treatment (persons with hematopoietic cell transplantation [HCT]).

Participants in this study will be randomized either to a control group, where they will wear the Fitbit® and provide daily reports of HRQOL over a three-month (90 day) period (without the personalized feedback), or the JITAI group, where they will wear the Fitbit®, provide daily reports of HRQOL and receive personalized pushes for 3 months. 60-90 participants will be enrolled (n=20-30 care partners of persons with SCI; n=20-30 care partners of persons with HD; and n=20-30 care partners of persons with HCT). Half of the care partners of each condition will be randomized into the JITAI group and half of the care partners of each condition will be randomized in the control group.

We hypothesize that this intensive data collection protocol will be both feasible and acceptable for care partners, and that the intervention will have a positive impact on care partner mood (strain, depression and anxiety).

**Objective:**

**Primary Objective:** To establish feasibility and acceptability of our intensive data collection protocol.

**Endpoints:**

**Primary Endpoints:** Feasibility and Acceptability as measured by the responses on the individual items on the Feasibility Questionnaire (items are scaled from 1 to 5 to indicate level of agreement, where "1" indicates "strong disagreement" and "5" indicates "strong agreement").

**Secondary Endpoints:** 1) Attrition as measured by the percent of participants completing the study; and 2) Adherence as measured by the percentage of missing data over the course of the study.

**Study Population:** 20-30 care partners of person with SCI, 20-30 care partners of persons with HD and 20-30 care partners of persons with HCT will participate in this study. Participant recruitment and enrollment will take place at the University of Michigan. Care partners must be at least 18 years old, be able to read and understand English and be caring for an adult (age 18 or above) with a medically documented diagnosis of SCI, HD or HCT. They must be willing to use their personal mobile device (e.g., smartphone, tablet) for this study, be willing to download the study app (CareQOL) and Fitbit® app and be willing to complete all study assessments.

**Phase or Stage:** Not applicable; behavioral intervention.

[figure not shown]
**Description of Sites Enrolling Participants:** There is one data collection site for this study: The University of Michigan in Ann Arbor, MI (n=20-30 care partners of person with SCI, n=20-30 care partners of persons with HD and n=20-30 care partners of persons with HCT).

**Description of Study Intervention:** Just-in-time adaptive intervention (JITAI) is a mobile health behavior-change approach that operationalizes the selection and delivery of personalized mobile device intervention strategies based on real-time data collection. In this study, a study-specific app (CareQOL app) will integrate sensor data from a Fitbit® (on physical activity and sleep) with real-time self-report ratings of HRQOL (caregiver strain, depression, anxiety) to inform the JITAI. The JITAI will deliver personalized messages via the app ~50% the days during the intervention period.

**Study Duration:** Data collection is expected to take 3 months.

**Participant Duration:** The participant duration in the study is ~100 days.

## 1.2 SCHEMA

### 1.3 SCHEDULE OF ACTIVITIES

	Pre-enrollment	Enrollment Day -10	~ 3 months 		
			Run-in  Days -10 to -1	End of months 1-2 assessments 30, 60 (+/- 7 days)	End of 3 month assessment  90 (+/- 7 days)
SCI/HD/HCT Documentation	X				
Caregiver Eligibility	X	X			
Informed Consent		X			
Demographics/Baseline Survey		X			
Caregiver Appraisal Scale		X			X
UHDRS Independence Scale		X			
SRS		X			
Medical Record Confirmation CRF		X			
HRQOL Measures		X		X	X
Fitbit® & CareQOL app Instructions		X			
Randomization		X			
JITIA  or Control Home Monitoring 			↔ →		
Daily EMA 			↔ →		
Feasibility/acceptability questionnaire					X
Medications/Therapies/Med History/COVID		X			X
Adverse Events Reporting					X
OPTIONAL: Semi-structured interview 					X

1 – Individual participant duration may vary depending on when they complete their HRQOL assessments; 2 – Approximately 10 days in duration, to include time for shipping and at least 3-4 days of data collection; 3 – Primary outcome assessment time point; 4 – Active intervention, includes personalized push notifications; 5 – Includes daily wearing the Fitbit® for sleep and physical activity monitoring for both groups; 6 – for both active and control groups; 7- Optional semi-structured interview for active group only; separate consent required

## 2 INTRODUCTION

### 2.1 STUDY RATIONALE

#### SIGNIFICANCE

Illness impacts the entire family, and the complete picture of human disease is a collage of the experiences of both the affected patient and family care partner(s). While significant scientific discoveries and advances in human health are prolonging life for individuals who previously may not have survived a serious illness or injury, the complexities of more advanced disease management and multifaceted care needs are also growing substantially. As a society, responsibility for addressing these needs has always been placed on family care partners, who face an enormous and growing burden providing care to a loved one while trying to maintain their own health and well-being (e.g., HRQOL).

While interventions exist to help improve these care partners' HRQOL, they are typically time-intensive and expensive, and have limited success at improving HRQOL in these individuals. Despite clear advantages in terms of convenience, reach and scalability with using mobile technologies (including JITAls) to support healthy behavior change, their clinical utility in care partners remains untested. Furthermore, while much research on care partners has focused on a one-size-fits all approach to assessment and treatment, there is a growing body of evidence to suggest that while there are many commonalities in the caregiver experience, there are aspects of care that are inherently unique to different caregiver groups. In order to better understand these commonalities and differences among different populations, this proposal includes *three distinct caregiving populations* designed to represent three different patient populations: 1) caring for a person with a chronic condition that was caused by a traumatic event (i.e., TBI); 2) caring for a person with a progressive, fatal neurodegenerative disease (i.e., HD); and 3) caring for a person with an episodic cancer condition that requires intense, prolonged inpatient and outpatient treatment (persons with hematopoietic cell transplantation [HCT]). These diverse caregiver groups not only allow for important between-population comparisons that can be used to inform future trial designs and maximize their impact; they also maximize the generalizability to other caregiving populations.

[figure not shown]
Specifically, this study is designed to establish the acceptability and feasibility of an intensive data collection protocol that involves passive mobile sensor data (using a Fitbit Charge®) and real-time patient-reported outcome (PRO) reports of symptoms and functioning (collected daily) in these three diverse caregiving populations.

### 2.2 BACKGROUND

#### Preliminary Studies.

*The proposed JITAl study methodology is modeled after and informed by the current findings from the Intern Health Study (R01MH101459; PI [name]).* In an early phase of the Intern Health Study, physical activity and sleep were assessed using Fitbit® Trackers, and daily ratings of mood were completed via text for N=38 medical interns. In this study, 92% of participants provided sleep, activity, and mood data on at least 80% of days. Data showed an expected strong association between sleep and mood, but found that sleep predicted mood the following day substantially more strongly than mood predicted subsequent sleep (Sleep→Mood  $b=0.12$ ;  $p<0.001$ ; Mood→Sleep  $b=0.05$ ;  $p=0.04$ ; **Figure**). They also found that, on a given night, the farther an individual's sleep midpoint was from their pre-internship baseline midpoint, the lower their mood ( $p<0.001$ ). In a more recent study phase (a randomized

controlled trial comparing a *JITAI* with usual care; n=2053), findings indicated that receptivity to mobile health interventions was moderated by participants' current state related to the target of the intervention. For instance, interventions around increasing sleep duration were most effective when participants had low sleep the night before, adding further conceptual backing for the *JITAI* approach. In addition, the *JITAI* intervention demonstrated significant improvements in depression.

## 2.3 RISK/BENEFIT ASSESSMENT

### 2.3.1 KNOWN POTENTIAL RISKS

The risks associated with the proposed study are minor and infrequent and include risks to: i) confidentiality; ii) frustration, stress and/or anxiety; iii) and skin irritation:

- i. **Confidentiality.** Confidentiality is a concern in this study. Every possible effort will be made to keep the research information in the strictest confidence, but we cannot absolutely guarantee that accidental disclosure will not happen. We remind participants that the responsibility of confidentiality rests with everyone: they should think carefully before discussing their role in this study with anyone since the effects of disclosure are unknown. Additionally, during the 3-month home monitoring period, participants may receive alerts when the participant is not in a private area. Participants will be informed that it is up to them where they complete the daily assessments, and if it is inconvenient/uncomfortable for them to complete the assessments when prompted they can wait and do it when it is more convenient/private or skip that assessment.

To reduce the risk to confidentiality, no personal identifying information will appear on or with the participant data, where possible. Each participant will be assigned a participant ID by the study team to maintain confidentiality. The participant's self-report data and CRF data will be identified with the participant ID. Additionally, an access code will be assigned

to each participant which they will use to enroll in the CareQOL app. Participants will register their study Fitbit® on the Fitbit® app using a username and email address of their choice. The study team will help the participant configure the Fitbit® app for minimal sharing; however, participants may opt to change those settings on their own (without study team knowledge). The data collected on the Fitbit® will be linked to the CareQOL app by user authentication token, which is comprised of a random series of characters that is used to securely query for user activity data; no identifying information (including email address or Fitbit® user ID) is saved in the CareQOL app.

The study team will keep a master list of participant names and matching participant IDs. This master list will not be shared outside of the study team, and will be kept by site personnel in a password-protected file on a secure server or in a secure environment (e.g., locked cabinet, restricted access). No one other than the study team will have access to their master list. Informed consents will be stored in a study-specific database which contains only the informed consents and the informed consents will only be available to the study team members. The electronic data collection and storage systems used (e.g., CareQOL app, REDCap, Qualtrics, Fitbit®) are secure, web-based systems, with access to the study data limited to authorized individuals.

Lastly, the identities of all participants will be held in strict confidence to the extent provided by law. If findings from the study are published and/or presented at a professional meeting, no participant will be identified by name.

- ii. Fatigue, Frustration, Stress and/or Anxiety. It is possible that participants may experience fatigue, frustration or feel inconvenienced when completing the self-report surveys, when receiving the personalized interventions from the CareQOL app or from wearing the Fitbit®. Participants may also feel fatigue, stress and/or anxiety related to completing the study activities. Participants will be instructed that they can skip any questions that make them feel uncomfortable, and if they receive an app alert when it isn't convenient for them, they can wait and open the app when it is more convenient.
- iii. Skin Irritation. Some participants may get skin irritation from wearing the Fitbit®. Participants will be instructed to remove the device if this occurs and to contact the study team. Their band may be swapped out for a different type of wristband if they experience irritation. We offer a wide variety of wristbands to help make the Fitbit® as comfortable as possible.

To minimize the potential for risks, participants will be briefed in detail as to what they will experience throughout the study. All participants are informed that they may terminate participation from the study at any time without penalty.

### 2.3.2 KNOWN POTENTIAL BENEFITS

The proposed study aims to investigate the feasibility and acceptability of an intensive data collection protocol that involves the administration of the JITAI intervention in care partners of persons with

significant health conditions. While there may not be any direct benefits to participants, it is possible that participants may find that the JITAI improves their mood, stress levels, and/or overall quality of life. Additionally, some participants may also have a positive benefit from wearing the Fitbit®, as it may make them more aware of their activity levels and sleep. Overall, we expect that the findings from this study will help researchers further develop a personalized, easy to deploy, clinical intervention for care partners of persons with significant health conditions.

### 2.3.3 ASSESSMENT OF POTENTIAL RISKS AND BENEFITS

As described above, there are minimal risks for the study participants and several potential benefits. Thus, the risk/benefit ratio is highly favorable.

## 3 OBJECTIVES AND ENDPOINTS

Objectives	Endpoints
Primary	
Primary Endpoint: Feasibility and Acceptability as measured by the responses on the individual items on the feasibility and acceptability questionnaire
 
Secondary Endpoint: Attrition as measured by the percent of participants completing the study
 
Secondary Endpoint: Adherence as measured by the percentage of missing data over the course of the study

To establish feasibility and acceptability of our intensive data collection protocol.	
Exploratory	
Change from baseline in self-reported strain as measured by Care-QOL Strain at the end of the 3-month (90 day) intervention period
 
Change from baseline in self-reported depression as measured by PROMIS Depression at the end of the 3-month (90 day) intervention period
 
Change from baseline in self-reported anxiety as measured by PROMIS Anxiety at the end of the 3-month (90 day) intervention period

Examine the impact that the JITAI has on improving self-reported mental health (caregiver strain, depression and anxiety) in care partners.	

## 4 STUDY DESIGN

### 4.1 OVERALL DESIGN

**Study Design:** This behavioral trial will use a two-arm randomized controlled design. Each of the 60-90 care partner participants will be randomized to an active “JITAI” arm (n=10-15 care partners of SCI, n=10-15 care partners of HD, n=10-15 care partners of HCT) or to a control arm (n=10-15 care partners of SCI, n=10-15 care partners of HD, n=10-15 care partners of HCT). The random allocation of participants to the treatment arm or control arm establishes the basis for testing the statistical significance or difference between the groups.

**Randomization:** Blocked randomization will be used to limit bias and achieve an equal distribution of participants to the control and treatment arms. A randomization list will be generated for each condition (SCI, HD, HCT) and the study statistician will oversee randomization. The participant will be randomized once he/she is deemed eligible and has provided informed consent (i.e. at enrollment prior to baseline data collection). The study coordinator/research assistant who consented the participant will use the appropriate condition’s randomization list to assign the participant to the correct study arm.

**Duration of Study Participation:** Study participation for both arms of the study (control and JITAI) involves a baseline assessment, followed by an approximate 10-day run-in period then a 3-month (90 day) home monitoring period (in which the intervention will be administered to the JITAI group). Thus, the total duration of the study is ~100 days.

**Study Sites:** This is a single-site study at the University of Michigan.

**Study Intervention:** The just in time adaptive intervention (JITAI) uses sensor data derived from the Fitbit® (e.g., accelerometer-based estimates of physical activity and sleep) and real-time self-report ratings (assessed once daily) of HRQOL (caregiver strain, depression, anxiety) to deliver personalized “pushes” to participants via a study specific app (CareQOL app). The personalized pushes will be delivered on ~50% of the days over the 3-month intervention period.

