## 6.2 FIDELITY

For this study, the intervention will be administered via the CareQOL app. The study team will conduct training during the baseline visit with each participant which will include:

- Helping the participant download and register for the CareQOL and Fitbit® apps on their personal device
- Helping the participant set any relevant app settings (e.g., make sure alerts are turned on/off, privacy settings, etc.)
- Demonstrating the CareQOL app features to the participant (e.g., participant dashboard, etc.)

- Ensuring that the participant understands the importance of entering the daily ratings and wearing the Fitbit®
- Explaining the relationship between the daily ratings and Fitbit® data and the intervention prompts (JITAI group only)
- Demonstrating how to sync the Fitbit® (including using the Fitbit® app) and how to enter the daily ratings in the CareQOL app

During the 10-day run-in period between the baseline visit and the start of the intervention, study team members will assist participants to make sure that participants can:

- Successfully wear and sync the Fitbit®
- Successfully respond to the EMA prompts

Participants who are unable to successfully complete the run-in period will be terminated from the study and noted as a screen failure.

Training and training materials will be provided to all study team members. New study members will undergo training before the study is started. Training will be documented in the electronic regulatory binder.

Participant adherence to the protocol will be assessed throughout the study. Study staff will have access to the CareQOL app dashboard which can be used to monitor participant engagement and adherence with the app. Specifically, study staff will monitor:

- Adherence to EMA entry
- Adherence to Fitbit® use/syncing
- Adherence to completing the end of month surveys (~30, 60, 90 day)

Adherence will be calculated as a percentage for each of these areas for all participants who are not withdrawn or lost to follow-up.

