### **8.1.2 CARE PARTNER ELIGIBILITY**

Confirmation of care partner eligibility according to criteria listed in Section 5, above, will be documented on the Eligibility CRF. It will occur prior to informed consent being obtained and before any study procedures associated with baseline assessment. Eligible individuals will then participate in the consent process, followed by randomization and baseline data collection.

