#### **8.1.4.3 RUN-IN HOME MONITORING PERIOD**

A 10-day run-in period will follow the baseline assessment. This period is to allow shipping time of the Fitbit® and provide the participant time to familiarize themselves with the study technology (Fitbit®, CareQOL app) and procedures. This period will also allow the study team to troubleshoot any potential barriers or issues that arise before the official start of the 3-month (90 day) home monitoring period. It also allows for data collection that can be used to inform the intervention messages once the home monitoring period begins.

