#### **8.1.5.1 BASELINE ASSESSMENTS**

Participants will be prompted by the CareQOL after registration to complete the baseline HRQOL assessments. Administration time is 10-15 minutes.

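### Randomisation comes before baseline and run-in, so baseline self-reports can be given with the arm known, and randomised run-in failures are labelled screen failures against the plan's own definition

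*Combined protocol and SAP*

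**What the plan says.** **Order of events.** Section 4.1 places randomisation after eligibility and consent, "i.e. at enrollment prior to baseline data collection". Section 8.1.2 agrees: "Eligible individuals will then participate in the consent process, followed by randomization and baseline data collection". Under 8.1.5.1, "Participants will be prompted by the CareQOL after registration to complete the baseline HRQOL assessments", and under 8.1.4.3, "A 10-day run-in period will follow the baseline assessment". The schedule in 1.3 puts consent, HRQOL measures and randomisation in one enrolment column, so it neither contradicts nor refines this order. Section 4.1 has the staff member who took consent assign the arm from the list. Section 6.2 lists, as part of baseline-visit training, "Explaining the relationship between the daily ratings and Fitbit® data and the intervention prompts (JITAI group only".

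**Run-in failures.** During the run-in, staff check that participants can "Successfully wear and sync the Fitbit" and "Successfully respond to the EMA prompts". Section 6.2 then says: "Participants who are unable to successfully complete the run-in period will be terminated from the study and noted as a screen failure". Section 5.4 defines a screen failure as someone who consents but is then not assigned to the intervention or not entered in the study. Section 7.1 describes people who do not complete the run-in as randomised and replaces them. It also replaces anyone who leaves before the end of home monitoring.

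**Analysis.** Section 9.1 expects at least 80% of participants to complete the study. Section 9.4.3 divides those completing the final assessment by those who completed baseline. Section 9.3 applies intention to treat to the exploratory analyses, however short a person's participation, and says attrition is estimated across the full sample, which it gives as N=60. Section 10.1.3 retains the data of people who withdraw.

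**The concern.** Two separate things are at stake.

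First, strain, depression and anxiety are self-reported, and their baseline values are subtracted in all three exploratory change scores (section 3). If a care partner knows the arm when answering, baseline may depend on it. The between-arm baseline tests in 9.4.4 could show an imbalance but could not tell a reporting effect from chance.

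Second, the run-in tests the behaviour this feasibility study sets out to judge: wearing and syncing the device and answering daily prompts. People who fail it are those for whom the protocol worked least. They are already randomised, yet they receive a label that section 5.4 reserves for people who never properly entered. If the label is used to drop them, the completion figure looks better than the experience of those enrolled.

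**Working it through.** **1. Can baseline depend on the arm?** Sections 4.1 and 8.1.2 fix the sequence as eligibility, consent, randomisation, baseline. Baseline HRQOL is prompted once the app is registered (8.1.5.1), and staff help with registration at the baseline visit, where the JITAI-only explanation is also given (6.2). No passage puts the HRQOL surveys ahead of that explanation, none says when participants learn their arm, and no masking is described. Dependence is therefore possible, though not shown.

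Let b0 and b90 be the shifts in reporting caused by knowing the arm, at baseline and at day 90. The change score then carries a bias of b90 − b0. Neither term can be obtained from the documents. If baseline is collected before the arm is known, b0 = 0 and the bias is b90. If the two shifts have the same sign they partly cancel under the present order, so net bias could rise after the change. The gain is a baseline that cannot depend on the arm.

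**2. Does the label fit?**
- 5.4: a screen failure was not assigned to the intervention or not entered.
- 4.1 and 8.1.4.3: anyone in the run-in has already been randomised and comes to it after the baseline assessment.
- 6.2: someone who fails the run-in is a screen failure.
- 7.1: someone who does not complete the run-in was randomised, and is replaced.
- 9.3: randomised people stay in their arm for the exploratory analyses.

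The first and third statements cannot both describe the same randomised person.

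**3. What could the label do to the completion figure?** The 80% expectation is not derived from other inputs, so there is no calculation to reproduce. The sample size is consistent with itself: 2 × 30 = 3 × 20 = 60, and 3 × (20 to 30) = 60 to 90. Run-in loss is not given, so every loss below is assumed.

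Let s be the number starting home monitoring, c the finishers, and b the run-in failures who completed baseline. Leaving run-in failures out gives c/s. Section 9.4.3 read literally gives c/(s + b). The literal rate falls below 80% when b > c/0.80 − s.

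| s | c | c/s | c/0.80 − s | smallest b | c/(s + b) |
|---|---|---|---|---|---|
| 60 | 49 | 81.7% | 1.25 | 2 | 49/62 = 79.0% |
| 60 | 51 | 85.0% | 3.75 | 4 | 51/64 = 79.7% |
| 60 | 54 | 90.0% | 7.5 | 8 | 54/68 = 79.4% |
| 60 | 57 | 95.0% | 11.25 | 12 | 57/72 = 79.2% |
| 90 | 77 | 85.6% | 6.25 | 7 | 77/97 = 79.4% |
| 90 | 81 | 90.0% | 11.25 | 12 | 81/102 = 79.4% |

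With fewer failures the conclusion is unchanged; for example, 51/63 = 81.0%.

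The same thing can happen if losses are replaced, as 7.1 directs, until 60 people finish. With 10 later losses and 6 run-in failures, all with baseline, the rate is 60/70 = 85.7% without the run-in failures and 60/76 = 78.9% with them.

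Someone randomised who never completes baseline falls outside the 9.4.3 denominator on either reading.

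**The case against.** The strongest reply is that the denominator is already settled. Section 9.4.3 is the only passage that defines the attrition calculation, and it uses baseline completers. A reader might infer from 9.3 that a rival denominator of 60 exists, or that replacement drives completion to 60/60. The documents do not support that. The reference to the full sample most naturally means both arms pooled, in line with the hypotheses in 9.1, which apply whichever group a person is in. The N=60 looks like a leftover: the synopsis and 4.1 plan 60 to 90, and the amendment history lists only 1.1 and 4.1 as updated. Replacement is a recruitment rule and removes no data, and 10.1.3 keeps the data of those who withdraw. This part of the reply stands. What remains is narrower: 9.4.3 counts study participants, and someone noted as a screen failure may be argued not to be one.

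It is also fair that 80% is an expectation for a secondary endpoint with no go/no-go rule attached, that every run-in loss used here is assumed, and that the 51-of-60 example leaves nine non-finishers unreplaced. The replacement example avoids that last difficulty.

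On the order of events, a reader might infer that the exploratory results will be biased towards the JITAI. The documents do not show this. They do not establish that participants know their arm when they answer; 6.2 lists registration before the JITAI-only explanation but sets no order; and the manual of procedures described in 10.1.5, which may specify the sequence, is not in the file. Participants receiving messages could hardly be masked later in any case. The point that survives is that nothing in the plan prevents it.

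**Conclusion.** The point holds in two limited parts.

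- **Order.** As written, self-reported baseline can be given with the arm known. Only the exploratory change scores are exposed. No size or direction can be given for the bias, and the primary endpoint is not affected by this order.
- **Label.** Calling randomised run-in failures screen failures contradicts 5.4 and fits poorly with 9.3. The literal text of 9.4.3 already counts those with a baseline assessment, so the weakness is that the label could be used to set them aside. Under assumed losses this decides whether 80% is reached: with 60 starters, between 2 and 12 such people are needed as finishers run from 49 to 57. With smaller losses it makes no difference. Run-in failures do not reach the day-90 questionnaire, so the label does not alter the primary endpoint's responses.

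This is worth fixing because the remedy is standard and cheap. It does not undermine the study's main aim.

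**What to change.** - **4.1, 8.1.2 and 1.3:** complete baseline HRQOL and the Caregiver Appraisal Scale before randomisation, or at least before the arm is revealed. In 6.2, give the JITAI-only explanation afterwards. Messages begin only after the run-in (6.1), so nothing else described for the run-in needs the arm. Randomising at the end of the run-in is an option if enrolment has not begun; if it has, that move would split a pilot of 60 to 90 people between two procedures.
- **5.4, 6.2 and 7.1:** stop calling randomised people screen failures, and state that replacement removes no one from the intention-to-treat set.
- **9.3 and 9.4.3:** confirm that the attrition denominator is everyone who completed baseline, including run-in failures and people later replaced, and report run-in losses by arm.

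Cost: one amendment, a small change in visit order, and a completion figure that may be slightly less favourable. No participants or assessments are added. Limit: collecting baseline before the arm is known removes only the baseline part of any reporting bias; the day-90 part stays.
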